## 2.5 Baseline Values and Subject Characteristics

Subject characteristics variables, such as demographic data, will be presented by descriptive statistics. Other measures taken at baseline, including medical history, and concomitant medication/procedures, will also be presented as appropriate using the ITT analysis set.

## 2.6 Analysis Populations

The following analysis sets will be defined:

- Safety analysis set Includes all subjects who were injected in at least one NLF, based on the as treated principle.
- Intention To Treat (ITT) Includes all subjects who were injected in both NLFs. Subjects are analyzed according to the randomization assignment.
- Per Protocol (PP) Includes all ITT subjects who completed the VAS assessment at injection without any deviations considered to have substantial impact on the primary efficacy outcome.

The ITT population is the primary population for all efficacy analyses. All safety analyses will be based on the Safety population.

## 2.7 Handling of Missing Data

As the design is intra-individual, in which the outcome of both treatments to be compared is available on each subject, it is expected that when a data is missing, it will be missing for both NLFs in most of the cases. A majority of the deviations to the protocol can be expected to affect both NLFs and evaluations of the same subject the same way.

ITT analysis of VAS at the time of injection will impute a difference (Restylane-Restylane Lidocaine) of 0 mm as the primary method of imputation. This corresponds to assuming no pain relief using Restylane Lidocaine compared to Restylane and is considered as a worst case approach. All other endpoints will be analyzed on available data, i.e. no imputations will be done.

	
Title 43CH1504 Restylane Lido Statistical Analysis Plan
	
Doc id MA-28883

--	--	-----------------------------------

Effective date: 2016-05-04 09:07

Effective

Version: 1.0

## 2.8 Efficacy Analysis

### 2.8.1 Primary analysis

The proportion of subjects that have a within-subject difference in VAS (Restylane-Restylane Lidocaine) of at least 10 mm at the time of injection will be calculated together with a two-sided 95% confidence interval. The objective is to show that the confidence interval lies above 50% based on the ITT analysis set. To assess the robustness of the results, the same analysis will be re-run using the PP analysis set.

The calculation of this proportion utilizes the split-face design of the study since it is based on within-subject difference in pain. The limit of 50% is chosen in order to show that the majority of subjects have at least 10 mm less pain when treated with Restylane Lidocaine as compared to Restylane.

[figure not shown]

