10.4 Efficacy Analysis

Primary analysis

[figure not shown]
The proportion of subjects that have a within-subject difference in VAS (Restylane-Restylane Lidocaine) of at least 10 mm at the time of injection will be calculated together with a two-sided 95% confidence interval. The objective is to show that the confidence interval lies above 50% based on the ITT analysis set. To assess the robustness of the results, the same analysis will be re-run using the PP analysis set.

CCI [REDACTED]

Secondary analysis

The proportion of subjects that have a within-subject difference in VAS of at least 10 mm at post injection timepoints (15, 30, 45 and 60 minutes after injection) will be calculated together with a two-sided 95% confidence interval.

CCI

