## 1 Study Information

### 1.1 Introduction

This is a randomized, multi-center, subject-blinded and evaluator-blinded study in China to evaluate the pain and the safety profile associated with correction of moderate to severe nasolabial folds (NLFs) using Restylane Lidocaine compared to Restylane. Approximately 70 subjects will be randomized to be treated with Restylane Lidocaine in one NLF and Restylane in the other, thus it is a split-face design. The study subjects will be treated at the baseline visit and thereafter followed for 2 weeks.

For more information regarding the study, please refer to the study protocol.

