## 2 Statistical Methods

### 2.1 General

All statistical analyses, including summary tables and data listings, will be performed using the SAS® system (version 9).

Confidence intervals will be 2-sided and made at the 95% confidence level. **CCI**

Continuous or semi-continuous variables will be summarized using descriptive statistics, e.g. mean, median and standard deviation. Categorical variables will be presented in frequency tables with number (n) and percent of observations for each level. All study data will be listed in subject listings.

Baseline value is defined as the latest measurement taken prior to treatment on Day 1.

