### 2.8.2 Secondary analyses

The secondary analyses will be carried out using the ITT analysis set, and will be descriptive in nature.

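### Does it matter that the readable plan does not name the type of 95% interval behind the primary success rule?

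*SAP*

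**What the plan says.** The primary rule appears in the objectives and analysis sections of both documents. In SAP 2.8.1 the responder proportion at injection "will be calculated together with a two-sided 95% confidence interval. The objective is to show that the confidence interval lies above 50" per cent. Protocol 10.4 puts it as "The objective is to show that the confidence interval lies above 50% based on the ITT analysis set". SAP 2.8.1 gives the reason for the threshold: "The limit of 50% is chosen in order to show that the majority of subjects have at least 10 mm less pain". On intervals in general, SAP 2.1 says "Confidence intervals will be 2-sided and made at the 95% confidence level". None of these passages names Wald, Wilson, exact or any other method.

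Other parts of the plan limit what is left open:

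- **Sample size.** SAP 1.1: "Approximately 70 subjects will be randomized to be treated with Restylane Lidocaine in one NLF and Restylane in the other".
- **Analysis set.** The ITT definition in SAP 2.6 reads "Includes all subjects who were injected in both NLFs", so the final n may differ a little from 70.
- **Missing primary outcome.** SAP 2.7: "ITT analysis of VAS at the time of injection will impute a difference (Restylane-Restylane Lidocaine) of 0 mm as the primary method of imputation". A missing subject therefore counts as a non-responder, and the denominator stays at the ITT number.
- **Other analyses.** SAP 2.8.2: "The secondary analyses will be carried out using the ITT analysis set, and will be descriptive in nature". Protocol 10.7 plans no interim analysis, and the per-protocol run is a robustness check.

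Parts of the text are blacked out. Protocol 10.1 has redactions inside its sentence on confidence intervals. SAP 2.1 has one directly after its sentence, and Protocol 10.4 has one after the primary analysis. The sample-size sections (Protocol 10.10 and SAP 2.11) are wholly redacted, and a figure after SAP 2.8.1 is not shown.

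**The concern.** The trial has one confirmatory decision: does the lower 95% limit for a single proportion exceed 50%? For a binomial proportion there are several 95% intervals in common use, and with about 70 subjects they do not always agree at the boundary. If the method is open, the same data could in principle be called a success under one interval and a failure under another, with the choice made after the data are seen.

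The simplest of these intervals also falls short of its nominal level here. A two-sided 95% rule implies a 2.5% chance of a false success at a true proportion of exactly 50%, and the Wald interval exceeds this at n = 70. At stake would be both the pre-specification of the primary analysis and its error rate.

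**Working it through.** **Inputs.** n = 70 (SAP 1.1), null proportion 0.50 (SAP 2.8.1), two-sided 95% so z = 1.96 (SAP 2.1), one look (Protocol 10.7). The earlier US trial's 71.7% of 60 subjects (Protocol 2.4.2), which is 43/60, is used only for context. The sample-size calculation is redacted, so there is no figure of the plan's own to reproduce.

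**Step 1: lower limits at 43 of 70.** The observed proportion is 43/70 = 0.6143.

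- Wald: p − z√(p(1 − p)/n). The standard error is √(0.6143 × 0.3857/70) = 0.0582, so the limit is 0.6143 − 1.96 × 0.0582 = 0.5003. This is a success, by a hair.
- Wilson: the lower limit exceeds 0.5 only if (x − n/2)/√(n/4) exceeds 1.96. Here (43 − 35)/√17.5 = 8/4.183 = 1.91, so it fails. The limit itself is 0.4972.
- Clopper-Pearson: the lower limit exceeds 0.5 only if P(X ≥ x | n, 0.5) is below 0.025. P(X ≥ 43 | 70, 0.5) = 0.0361, so it fails. The limit is 0.4903.

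The Agresti-Coull (0.4970), Jeffreys (0.4975), mid-P (0.4967) and continuity-corrected Wald (0.4931) limits fail as well. The uncorrected Wald interval stands alone.

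**Step 2: lower limits at 44 of 70.** Wald gives 0.5154, Wilson 0.5115 and exact 0.5048. All succeed, and P(X ≥ 44 | 70, 0.5) = 0.0207.

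At n = 70 the one-sided error is therefore 3.61% with Wald and 2.07% with Wilson or exact. By symmetry the Wald coverage at 50% is 1 − 2 × 0.0361 = 92.8%.

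**Step 3: how often the choice would decide the result.** Only x = 43 is affected, so its probability is the difference in power between the two cut-offs.

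| True rate | P(X ≥ 43) | P(X ≥ 44) | P(X = 43) |
|---|---|---|---|
| 50% (null) | 3.61% | 2.07% | 1.5% |
| 60% (assumed) | 45.5% | 36.0% | 9.5% |
| 65% (assumed) | 77.5% | 69.5% | 8.0% |
| 71.7% (earlier trial) | 97.7% | 95.9% | 1.8% |

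The maximum over all true rates is about 9.8%, near 61%. At the earlier trial's own result, 43/60, the lower limits are 0.603 (Wald), 0.592 (Wilson) and 0.586 (exact), all far above 0.50.

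**Step 4: other values of n.** Each cell gives the smallest successful count, with the one-sided error at 50%.

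| n | Wald | Wilson | Exact |
|---|---|---|---|
| 65 | 41 (2.32%) | 41 (2.32%) | 41 (2.32%) |
| 66 | 41 (3.20%) | 41 (3.20%) | 42 (1.78%) |
| 67 | 42 (2.49%) | 42 (2.49%) | 42 (2.49%) |
| 68 | 42 (3.41%) | 43 (1.92%) | 43 (1.92%) |
| 69 | 43 (2.66%) | 43 (2.66%) | 44 (1.47%) |
| 70 | 43 (3.61%) | 44 (2.07%) | 44 (2.07%) |
| 71 | 44 (2.84%) | 44 (2.84%) | 45 (1.60%) |
| 72 | 45 (2.22%) | 45 (2.22%) | 45 (2.22%) |
| 73 | 45 (3.02%) | 45 (3.02%) | 46 (1.72%) |
| 74 | 46 (2.37%) | 46 (2.37%) | 46 (2.37%) |
| 75 | 46 (3.20%) | 46 (3.20%) | 47 (1.85%) |

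The three methods never differ by more than one responder, and they agree fully at 65, 67, 72 and 74. Wald and Wilson part only at 68 and 70. The 3.61% at n = 70 is the largest Wald error in this range.

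**The case for a change.** The strongest case for a change is that a sole success criterion should leave nothing to choose, and that one sentence would settle it. The two paragraphs of SAP 2.8.1 read as continuous text with no redaction mark, and the list of changes in SAP 2.12 mentions only the SAS version. The effect is not confined to n = 70 either: Wald and exact cut-offs differ at seven of the eleven values from 65 to 75, and the Wald error exceeds 2.5% at each of the seven. If the true rate were in the low sixties, the boundary outcome would have a probability of nearly one in ten. Only the exact interval holds 2.5% at every n in the table.

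The arithmetic in that case stands. Three things weaken the conclusion drawn from it. First, the method may be written under the redactions, and text that is blacked out cannot be counted as missing. Second, the complaint about the error rate applies to a rule that the plan does not state, since nothing readable points to Wald. Third, exact against Wilson is partly a matter of preference: at 70 they give the same cut-off, error and power, and elsewhere they differ by at most one responder. Nor is the stricter cut-off always cheap. Moving from 43 to 44 costs about 2 points of power at 71.7%, but 8 points at an assumed 65%. The 71.7% is an earlier trial's result, not a stated planning assumption.

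**Conclusion.** No change to the plan is needed. The readable text leaves the interval method open, but it fixes what matters most: the proportion, the threshold, the level, the sidedness, the analysis set and the handling of missing values. What remains is a technical detail that a trial statistician would normally fill with an exact or Wilson interval, and at n = 70 either gives the rule of 44 responders with a one-sided error of 2.07%.

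The exposure is one outcome, 43 of 70. It has a probability of about 1.8% if the earlier US rate of 71.7% holds, and at most about 9.8% otherwise. At worst, with Wald at exactly 70 subjects, the one-sided error would be 3.6% instead of 2.5%. The 15 to 60 minute proportions are descriptive, so the choice of interval has no bearing on error control there.

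This rests on a final n close to 70 and on the readable text alone. If the redacted text names a method, the question of discretion disappears. If that method were Wald, the modest error excess shown above would remain.

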### 2.8.2 Secondary analyses

The secondary analyses will be carried out using the ITT analysis set, and will be descriptive in nature.

#### VAS assessments

The proportion of subjects that have a within-subject difference in VAS of at least 10 mm at post injection time points (15, 30, 45 and 60 minutes after injection) will be calculated together with a two-sided 95% confidence interval.

CCI

## 2.9 Safety Analysis

All safety evaluations will be performed based on the safety analysis set.

AEs will be summarized in frequency tables by group, presenting number of subjects with no AEs and subjects with at least one AE subdivided by related/unrelated, and serious/non-serious. All AEs will be summarized and listed by SOC and PT assigned using MedDRA. Furthermore, AEs will be summarized by causality and maximum intensity. For related AEs the number of days to onset and the duration of the event will be summarized by PT.

All AEs will be included in the data listings. Any serious adverse events and/or AEs that led to withdrawal will be listed separately.

	
Title 43CH1504 Restylane Lido Statistical Analysis Plan
	
Doc id MA-28883

--	--	-----------------------------------

Effective date: 2016-05-04 09:07

*Effective*

Version: 1.0

CCI

## 2.10 Interim Analysis

Not applicable.

## 2.11 Determination of Sample Size

CCI

## 2.12 Changes in the Analysis planned in the Clinical Study Protocol

In CSP it was stated that all statistical analyses will be performed using the SAS® system, version 9.0. This is an old SAS® version, and a newer one will be used.

CSP text: “All statistical analyses, including summary tables and data listings, will be performed using the SAS® system (version 9.0).”

New text in this SAP: “All statistical analyses, including summary tables and data listings, will be performed using the SAS® system (version 9).”

